## **9. Withdrawal**

Participants will have the option to withdraw from the treatment or the study at any time. Those withdrawing from the treatment will continue to be sent follow-up questionnaires unless they specifically request not to receive them. Failure of any participant to complete a follow-up questionnaire at any particular time-point will not be counted as a withdrawal unless the participant requests not to receive any further follow-ups.

## **10. Statistical Issues**

### *Sample Size*

Our previous longitudinal study of onset of CWP (and subsequent replication) has suggested that 21% of "high risk" persons identified will develop CWP over the course of the next twelve months. Our previous data is based on persons with pain and at least 2 out of 3 other "risk factors". There are no published studies of prevention of CWP on which to base our measure of effect. However in the MUSICIAN study some subjects, although reporting CWP at the screening survey, no longer had CWP at the enrolment interview. They were however still eligible to take part, provided they had regional pain. Therefore those subjects with regional pain provide a sub-population on which to base the likely effects of the tCBT. Amongst such subjects, those who received tCBT had a reduced odds of having CWP at the end of the study OR 0.5 95% CI (0.2-1.4) compared to those in usual care.

Thus the study is powered on the ability of the current study to reduce the onset of CWP from 21% to 12%, with 90% power and a 5% significance level. We further assume, based on prior data, that 75% of persons allocated to the tCBT arm will be adherent to the intervention, and that 80% of all subjects will return the follow-up questionnaires to assess outcome.

Accordingly we require 473 subjects per arm that is a total of 946 subjects recruited. In MUSICIAN exactly 50% of those found eligible and willing to consider taking part ultimately were randomised. A previous trial of a cognitive-behavioural intervention to prevent chronic pain found that 36% of patients identified as eligible ended up being recruited to the study (13). If 84% of eligible patients agreed to be contacted about taking part, this equates to 43% of those eligible and willing to consider taking part being randomised - higher numbers for a clinical trial of CWP reflect the fact that this is a prevention trial rather than a treatment trial and may be less attractive to potential participants. Thus we aim to find

a total of 2,200 subjects who are eligible and willing to consider taking part. Assuming a participation rate to the survey of 24%, that 18% people will be "at risk", and that 84% of people who return a questionnaire agree to consider taking part, we require to survey 60,625 persons.

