A systematic review and meta-analysis of randomised controlled trials (RCT) of Cognitive Behaviour Therapy (CBT) for patients with fibromyalgia concluded that CBT improves coping with pain, reduces depressed mood and healthcare-seeking behaviour in such patients (9). The delivery of CBT by telephone has been shown to be effective, acceptable and accessible (10). The MUSICIAN study, which we have recently concluded, tested telephone delivered CBT (tCBT) and/or exercise for patients with chronic widespread pain consulting to their GP (using a 2 x 2 factorial design). Three months after the end of therapy, both interventions resulted in significantly better primary outcome measures (patient global health) than treatment as usual (tCBT 33% of participants with positive outcome, exercise 24%, treatment as usual 8%), but there was no significant additional benefit of receiving both interventions (combined 37%). Recent analyses have demonstrated these benefits are maintained 2 years after the end of therapy (11): tCBT 35% with positive outcome, exercise 29%, combined 31%, treatment as usual 13%. We have conducted a comprehensive literature review with the aim of identifying randomised trials which had the aim of preventing the onset either of CWP or fibromyalgia. This review did not identify any such published trials. Further, a search of 11 international clinical trials registers/databases (including US, UK, Europe, Australia/New Zealand, Japan), undertaken in Autumn 2013 did not identify any ongoing trial with the aim of preventing the onset of CWP (or fibromyalgia).

There are several reasons why it may be desirable to try to prevent CWP onset, namely that the majority of CWP patients do not have important symptom improvement with current management (even within trials). Prediction models from epidemiological studies have been developed to identify “high risk” patients, which makes such an approach feasible. Research using the General Practice Research Database (GPRD) has demonstrated that prior to receiving a diagnosis of fibromyalgia in primary care, persons have a long-term prior history of consultation with symptoms (12). Although this will be the first prevention trial in this area, the concept of prevention using CBT has been addressed in musculoskeletal disorders with respect to intervention in neck pain and low back pain before people become patients (13) and in mental disorders (14).

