### *Statistical analysis*

A pre-defined statistical analysis plan will be developed and signed off by the trial steering committee before undertaking any data analysis. Comparison between arms will be on an intention-to-treat basis (main analysis) with a per protocol sensitivity analysis.

Characteristics of the study participants in the two treatment arms will be described using simple summary statistics. Descriptive statistics will include mean and standard deviation for normally distributed continuous data, median and inter-quartile range for skewed continuous data and count and percentage for categorical data. No formal statistical comparisons will be made between baseline characteristics. Primary and secondary outcomes will be described at the three follow-up times: 3, 12 and 24 months, using appropriate summary statistics. The primary outcome is the between arm difference in the proportions of people developing CWP from baseline to follow-up. This comparison will be made using simple chi-squared tests at each follow-up time. Appropriate adjustment will be made for the stratification factor used in the randomisation (the number of non-pain "high-risk" factors that a participant reports at baseline) using multiple logistic regression.

Comparisons with appropriate hypothesis tests will be used for the secondary outcomes, pain, illness behaviour, somatic symptom reporting, sleep problems, quality of life and wellbeing, psychological distress, patient global impression of change measure and fatigue. Appropriate adjustment will be made for the stratification factor. Given the multiple secondary outcomes, the p-value used to denote statistical significance will reflect the multiple comparisons.

Mixed models analyses with an appropriate error structure will take into account the repeated assessment of the outcome data for the same patient across the three follow-up times. As part of sensitivity analyses, multiple imputation methods will be used, where appropriate, to address issues of missing data. However, these methods will not be applied if the use of imputation is contrary to specified rules for the relevant validated measurement scale.

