2. ANALYSIS

2.1. STUDY POPULATIONS

Comparison between arms will be on an intention-to-treat basis (main analysis) with a per protocol sensitivity analysis.

Intention to treat (ITT) population

Intention to treat analysis will be of all participants who were randomised and for whom at least one follow-up observation of the primary outcome is available. Participants will be analysed in the group to which they were randomised.

[figure not shown]
Per protocol (PP) population

Pre protocol analysis will be of all participants of the ITT population excluding participants who were not compliant with their randomised study arm. Non-compliance is defined as those not having any primary outcome data and/or those not completing treatment as in the definition below.

Full intervention will consist of an initial assessment (45-60 minutes), 6 weekly sessions (each 30-45 minutes) over six weeks, and then booster sessions at 3 and 6 months. The per protocol analysis will be those receiving the completed treatment (defined below) vs. all others.

A participant in the CBT group has completed treatment if: there is mutual agreement between therapist and participant to stop treatment AND at least one session (the initial assessment) has been attended; OR, participant has at least 3 sessions of CBT (including the initial assessment)

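### 75% adherence is listed as an input to 473 per arm, but at the printed rates 473 contains no allowance for it, and neither document says whether the 12% tCBT rate already includes non-adherence

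*Protocol*

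**What the plan says.** The sample size text is the same in Protocol section 10 (Sample Size) and SAP 1.4 on every point used here. The target effect is given first: "Thus the study is powered on the ability of the current study to reduce the onset of CWP from 21% to 12" per cent, with 90% power at the 5% level. Its only stated source is a subgroup of the earlier MUSICIAN trial, in which "those who received tCBT had a reduced odds of having CWP at the end of the study OR 0.5". Two assumptions follow: "We further assume, based on prior data, that 75% of persons allocated to the tCBT arm will be adherent to the intervention", and 80% of all subjects returning follow-up questionnaires. The next paragraph of the protocol draws the conclusion: "Accordingly we require 473 subjects per arm that is a total of 946 subjects recruited".

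No formula or continuity correction is mentioned. The sample size text gives no sidedness, but SAP 2.4.1 sets a two-sided 5% level.

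On analysis, both documents state: "Comparison between arms will be on an intention-to-treat basis (main analysis) with a per protocol sensitivity analysis". SAP 2.1 keeps participants in the arm to which they were randomised. It counts tCBT as completed if therapist and participant agree to stop after at least the initial assessment, or if the "participant has at least 3 sessions of CBT (including the initial assessment").

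**The concern.** The order of the text (effect, then two further assumptions, then the required number) tells the reader that 473 allows for both non-adherence and non-return. Under intention-to-treat, non-adherers stay in the tCBT arm. If 12% describes people who take up the therapy, the contrast actually tested is smaller than 21% v 12%, and the sample size must be larger to keep 90% power.

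The reader needs to know whether non-adherence is already inside the 12%, was added on top of it, or was not used. This governs how a null intention-to-treat result would be read: the planned 10% risk of missing the target effect could be about 20%, or about 35% at the extreme. Type I error and the reported estimate are not affected.

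**Working it through.** **Inputs.** Control rate p₁ = 0.21, tCBT rate p₂ = 0.12, power 90%, adherence 75%, return 80% (Protocol section 10, SAP 1.4); two-sided 5% (SAP 2.4.1). z = 1.960 and 1.2816.

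**Reproducing 473.** With p̄ = (p₁ + p₂)/2 = 0.165:

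n = [1.960·√(2p̄(1−p̄)) + 1.2816·√(p₁(1−p₁) + p₂(1−p₂))]² / (p₁ − p₂)²
= [1.960 × 0.5249 + 1.2816 × 0.5211]² / 0.09² = 355.4, so 356.

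Continuity corrected: (n/4)·[1 + √(1 + 4/(n × 0.09))]² = 377.3, so 378.

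- Return only, uncorrected: 356/0.80 = 445.
- Return only, corrected: 378/0.80 = 472.5, so **473**, which matches.

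**Adding 75% adherence at the printed 12%** (uncorrected to corrected, per arm):

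- Averaged over the arms, (0.75 + 1)/2 = 0.875 and 0.875 × 0.80 = 0.70: 508–540.
- Simple inflation, 0.75 × 0.80 = 0.60: 593–630.
- Dilution with no benefit in non-adherers, 0.75 × 12% + 0.25 × 21% = 14.25%: 668–697 analysed, 835–872 recruited.

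**One route that uses both percentages.** OR 0.5 applied to 21%: odds 0.21/0.79 = 0.2658, halved to 0.1329, giving 0.1329/1.1329 = 11.7%. At 11.7%, uncorrected, n = 330.2, so 331, and 331/0.70 = 472.9, so 473. This needs the unprinted rate rounded to 11.7%; the unrounded 11.73% gives 333/0.70 = 475.7, so 476. Averaging adherence over the arms also inflates the number without shrinking the effect, so it does not allow for intention-to-treat dilution.

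**What 473 delivers.** 473 × 0.80 = 378 analysed per arm.

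Power = Φ{[(p₁ − p₂) − c − 1.960·√(2p̄(1−p̄)/n)] / √([p₁(1−p₁) + p₂(1−p₂)]/n)}, with c = 1/n if corrected and 0 if not.

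- At 12%: corrected Φ(1.285) = 90.1%; uncorrected Φ(1.384) = 91.7%.
- Highest whole-arm tCBT rate that gives 90% power: 12.01% corrected, 12.25% uncorrected.

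Let a be the adherers' rate and f the share of the full benefit that non-adherers get (f is assumed; the documents give no value). The whole-arm rate is 0.75a + 0.25[21% − f(21% − a)].

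| Adherers' rate | f | Whole-arm rate | Power, corrected | Power, uncorrected |
|---|---|---|---|---|
| 12% | 1 | 12.00% | 90.1% | 91.7% |
| 12% | 0.5 | 13.13% | 79.6% | 82.2% |
| 12% | 0 | 14.25% | 64.9% | 68.3% |
| 11.7% | 1 | 11.70% | 92.1% | 93.4% |
| 11.7% | 0.5 | 12.86% | 82.4% | 84.8% |
| 11.7% | 0 | 14.03% | 68.1% | 71.4% |

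Share of benefit that non-adherers must keep (uncorrected to corrected):

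| Adherers' rate | For 90% power | For 80% power |
|---|---|---|
| 12% | 89–100% | 41–52% |
| 11.7% | 77–87% | 30–40% |

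**The case against.** The strongest reply is that 12% is the whole-arm rate. The target is worded as what the study will achieve. The earlier trial's results are reported by arm ("tCBT 33% of participants with positive outcome, exercise 24%, treatment as usual 8" per cent, Protocol section 3), and that section speaks of receiving an intervention when it describes trial arms, so the phrase about those who received tCBT need not mean those who adhered. On this reading non-adherence is already in the effect: for example, 0.75 × 9% + 0.25 × 21% = 12%. Power is then about 90%. This is a natural reading and it stands as a possibility. Neither document confirms it, and it leaves the adherence assumption redundant among the inputs.

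Second, the 75% may have been used, through 331/0.70, or may have been meant for the per-protocol analysis. The uncorrected route also fits the planned test ("This comparison will be made using simple chi-squared tests at each follow-up time"), and the continuity correction in the other route is no more printed than 11.7% is. So it cannot be asserted that 75% was left out. But neither use would protect intention-to-treat power from dilution.

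Third, the zero-benefit case is extreme, because under the SAP completion rule some non-completers may have had one or two sessions. That is right, and 65–68% is only a lower bound.

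A reader might infer that 473 is an arithmetic error or that the trial is underpowered. The documents support neither: 473 reproduces exactly at the printed rates, and the shortfall depends on a meaning of 12% that is not stated.

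**Conclusion.** The point holds as a defect in how the sample size is justified. 473 and 90% intention-to-treat power do not follow from the listed assumptions unless 12% already includes non-adherence, or non-adherers keep nearly all of the benefit.

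The size depends on what 12% means. As the whole-arm rate, it gives the stated power. As the adherers' rate, it gives about 80–82% with half the benefit in the rest and 65–68% with none; at 11.7% these become 82–85% and 68–71%.

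The figures assume 80% return in both arms and an invented benefit in non-adherers. They are two-proportion approximations to the planned 12-month logistic model, which adjusts for risk-factor count, age, sex and practice. The matter should be fixed because a relied-on figure cannot be traced to its stated inputs.

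**What to change.** In Protocol section 10 and SAP 1.4:

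1. State the formula used, including any continuity correction, and whether and where 75% enters 473. If it was not used, take it out of the inputs that precede the required number and say what it is for.
2. If 12% is the rate among all allocated to tCBT, say so, and say that non-adherence is already included. Nothing more is then needed.
3. If 12% is the adherers' rate, replace the 90% with a statement such as: With 378 analysed per arm, intention-to-treat power is about 80–82% if the 25% who do not adhere get half the benefit, and 65–68% if they get none (lower bound). The benefit in non-adherers is assumed, and these are two-proportion approximations to the adjusted logistic model. If 11.7% was the rate used, the figures are 82–85% and 68–71%.

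The cost is one paragraph in each document and, under item 3, a less favourable stated power. No extra participants are needed and the analysis does not change.

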### *Statistical analysis*

A pre-defined statistical analysis plan will be developed and signed off by the trial steering committee before undertaking any data analysis. Comparison between arms will be on an intention-to-treat basis (main analysis) with a per protocol sensitivity analysis.

Characteristics of the study participants in the two treatment arms will be described using simple summary statistics. Descriptive statistics will include mean and standard deviation for normally distributed continuous data, median and inter-quartile range for skewed continuous data and count and percentage for categorical data. No formal statistical comparisons will be made between baseline characteristics. Primary and secondary outcomes will be described at the three follow-up times: 3, 12 and 24 months, using appropriate summary statistics. The primary outcome is the between arm difference in the proportions of people developing CWP from baseline to follow-up. This comparison will be made using simple chi-squared tests at each follow-up time. Appropriate adjustment will be made for the stratification factor used in the randomisation (the number of non-pain "high-risk" factors that a participant reports at baseline) using multiple logistic regression.

Comparisons with appropriate hypothesis tests will be used for the secondary outcomes, pain, illness behaviour, somatic symptom reporting, sleep problems, quality of life and wellbeing, psychological distress, patient global impression of change measure and fatigue. Appropriate adjustment will be made for the stratification factor. Given the multiple secondary outcomes, the p-value used to denote statistical significance will reflect the multiple comparisons.

Mixed models analyses with an appropriate error structure will take into account the repeated assessment of the outcome data for the same patient across the three follow-up times. As part of sensitivity analyses, multiple imputation methods will be used, where appropriate, to address issues of missing data. However, these methods will not be applied if the use of imputation is contrary to specified rules for the relevant validated measurement scale.

## **11. Study Management and conduct**

### **11.1 Trial Steering Committee**

A trial steering committee (TSC) will be established and comprise an independent chair who has expertise in both trials and CWP and two other independent members including a user representative who has had lived experience of CWP and a clinician working with people with CWP.

### **11.2 Inspection of Records**

Investigators and institutions involved in the study will permit study related monitoring and audits on behalf of the sponsor and REC. In the event of an audit or monitoring, the Investigator agrees to allow the representatives of the sponsor direct access to all study records and source documentation, and participant consent will be obtained for this.

### **11.3 Confidentiality**

All evaluation forms, reports, and other records will be identified in a manner designed to maintain participant confidentiality. All records will be kept in a secure storage area with limited access.

### **11.4 Data Protection**

All Investigators and study site staff involved with this study will comply with the requirements of the Data Protection Act 1998 with regard to the collection, storage, processing and disclosure of personal information and will uphold the Act's core principles. Computers used to collate the data will have limited access measures via user names and passwords. Published results will not contain any personal data that could allow identification of individual participants.

### **11.5 Study Record Retention**

All study documentation will be kept for a minimum of 5 years from the protocol defined end of study point. When the minimum retention period has elapsed, study documentation will not be destroyed without permission from the sponsor.

### **11.6 End of Study**

The end of study is defined as data collection at 2 years from the last participant's date of beginning treatment or dummy treatment start date.

### **11.7 Reporting, Publication and Notification of Result**

Ownership of the data arising from this study resides with the University of Aberdeen. On completion of the study, the study data will be analysed and tabulated, and a clinical study report will be prepared in accordance with ICH guidelines.

The clinical study report will be used for publication and presentation at scientific meetings. Investigators have the right to publish orally or in writing the results of the study.

### **11.8 Insurance and Indemnity**

The University of Aberdeen is sponsoring the study.

Insurance:

- The University of Aberdeen will obtain and hold a policy of Public Liability Insurance of legal liabilities arising from the study.
- Where the study involves University of Aberdeen staff undertaking clinical research of NHS patients, such staff will hold honorary contracts with Grampian Health Board with means they will have cover under Grampian's membership of CNORIS scheme.

Indemnity:

The sponsor does not provide study participants with indemnity in relation to participation in the Study but has insurance for legal liability as described above.

1. INTRODUCTION

1.1. BACKGROUND

Chronic widespread pain (CWP), the characteristic feature of fibromyalgia, is associated with reduced productivity at work, mental ill health, and poor quality of life. Current guidelines recommend drug therapy, physical and psychological therapies, although different guidelines put different emphasis on how important each type of therapy is. There is good evidence that the longer a patient experiences an episode of pain, the less likely that symptoms are to improve. This is particularly true for CWP – so it is important to manage symptoms early or, better, to try to prevent onset. An Arthritis Research UK report on fibromyalgia/CWP, based on a think-tank held in July 2012 with patient input, identified prevention as a research priority. We have previously shown short and long-term effectiveness of CBT delivered by telephone (tCBT) for CWP in an Arthritis Research UK funded study and we have now developed effective ways to predict who is at high risk of developing CWP.

People who consult their general practitioner with musculoskeletal pain and who also have, in addition, at least two of the following characteristics are at high risk of developing chronic widespread pain (CWP), the main feature of fibromyalgia:

- disturbed sleep,
- several other bodily symptoms (apart from pain),
- specific beliefs about their symptoms (e.g. have strong worries or perceptions that their symptoms indicate a serious illness, even though this is not supported by clinical assessment)

1.2. STUDY OBJECTIVES

The primary objectives are:

We will test the hypothesis that among patients who report regional pain for which they have already sought a consultation in primary care, and who are identified as high risk of developing chronic widespread pain, a short course of telephone-delivered Cognitive Behaviour Therapy (tCBT) reduces the onset of CWP.

We will further determine the cost-effectiveness of such a preventative intervention.

We wish to find out whether, among patients identified as being at high risk of developing CWP, a short course of tCBT reduces the risk of CWP onset. We will determine during therapy/usual care (3 months after treatment/dummy treatment start date), after therapy has finished (12 months), and in the long-term (24 months) how many persons have developed CWP and whether this is different between the two treatment groups. The primary outcome is the between arm difference in the proportions of people developing CWP from baseline to 12 months. Appropriate adjustment will be made for the stratification factor used in the randomisation (the number of non-pain “high-risk” factors that a participant reports at baseline).

Secondary objectives:

We will also measure patients' overall perceptions of their condition, their quality of life, fatigue and psychological ill health, in order to get a full picture of the effects of the tCBT. Secondary outcomes will be described at the three follow-up times: 3, 12 and 24 months, using appropriate summary statistics.

Comparisons with appropriate hypothesis tests will be used for the secondary outcomes, pain,

illness behaviour, somatic symptom reporting, sleep problems, quality of life and wellbeing, psychological distress, patient global impression of change measure and fatigue. Appropriate adjustment will be made for the stratification factor. The baseline value of the relevant outcome variable will also be included as a covariate.

